5. STUDY DESIGN

5.1. General

The study is a multicenter, multi-case, multi-reader (MCMR) study with paired image acquisition and reader evaluation. The study will be performed in two phases: Imaging Accrual phase and Imaging Reading phase.

Approximately 800 women who fulfill all inclusion and exclusion criteria will be enrolled in chronological order from approximately 3 different US sites with one study investigator for each site. Two cohorts of patients will be enrolled (i.e., Biopsy and Screening Cohorts). Paired sets of a standard 4-view synthetic 2D and tomosynthesis slices exposed on Philips MicroDose Tomosynthesis system and 4-view mammograms on a FDA cleared FFDM system will be collected. All enrolled cases will be quality controlled for completeness of image and patient information.

A subset of the images collected as part of this study will also be used to validate the spectral breast density measurement. This validation is specified in a separate study protocol [9].

Depending on the experience at the sites, each site could also enroll up to 10 additional women to train the technologists on using the system and whose images will be used for training purposes. These cases will not be used in the reader study. In addition to these cases, images for reader training will be available that have been previously collected under another IRB approved protocol.

Approval for the study will be obtained from the ethics committees for all participating centers. All eligible subjects will provide written informed consent prior to entry into the study, which is defined as being imaged on the Philips MicroDose Tomosynthesis system and an FFDM system. Subject enrollment will be monitored by the sponsor at each site. All subjects will be consecutively enrolled.

All subjects interested in participating in the study will be assigned a unique study identification number. At the time of providing informed consent, subjects will be assigned the next number in sequence from the list of study identification numbers. After study enrollment, subjects will be identified solely by their study identification number on the Case Report Forms (CRF). In addition, all subject specific information will be removed from the images prior to them being electronically submitted to the study sponsor and only the subject's study identification number will be provided. Each participating site will maintain a database linking the study number to subject identification.

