5.5.3. Procedure Endpoint

- Radiation dose: Average Glandular radiation dose will be read out from the DICOM header for each mammogram.
- Image interpretation time: Interpretation time will be measured during the reading study for each reader. The interpretation time includes the time the reader takes reviewing the case and completing the case report form.

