6.1.2. Sample Size Justification for Average Glandular Dose

Another secondary objective of this study is to compare the average radiation dose between the Philips MicroDose tomosynthesis system and FFDM systems. Radiation dose will be evaluated based on the subject overall dose received during the examination. For the null hypothesis, no difference in radiation dose delivered to the patient during a mammographic exam between two systems, will be evaluated.

Using historical data from the study site, the average radiation dose per breast for 20 subjects, 2 sample (MLO + CC) was of 3.6 (standard deviation of 1.1), ranging from 2.4 to 6.7 for the GE FFDM, and of 2.6 (standard deviation of 0.7) ranging from 1.6 to 4.0 for Hologic mammography system. Also, in a previous study, comparing the three systems reported radiation dose per breast of 1.86, 2.91, and 3.03, for Philips MicroDose, Hologic and GE, respectively representing a reduction of radiation of approximately 40% for MicroDose compared to Hologic and or the GE mammography system.

Assuming that the standard deviation for the difference in radiation dose will be approximately 1.5mGy, a sample size of approximately 100 subjects will allow for greater than 80% power to detect a difference in radiation between the two systems of approximately 0.5mGy (i.e., 10% of the overall patient radiation) using a paired t-test with a 0.025 one-sided significance level.

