6.8. Secondary Efficacy Analysis

The secondary objectives are:

- To compare the average glandular dose for exams acquired on Philips MicroDose Tomosynthesis system and the 2D mammography system.
- To compare the non-cancer recall rate for Philips MicroDose Tomosynthesis system and 2D mammography exams.
- To compare the sensitivity and specificity of the Philips MicroDose tomosynthesis system (i.e., Tomosynthesis and synthetic 2D) to that obtained with 2D mammography.

Secondary objectives will only be tested if the null hypothesis for the primary endpoint is rejected. Four secondary endpoints will be evaluated. To control the Type I error, the following pre-specified order using a gatekeeper procedure as described by Dmitrienko et al. (2007) will be used:

Family	Endpoint	Procedure
F1	AUC ROC	Test at the 0.05 level, no adjustment to the p-value
F2	Radiation Dose	Test only if Ho for AUC ROC is rejected, p-value adjusted using HOLM procedure
	Recall Rate	Test only if Ho for AUC ROC is rejected, p-value adjusted using HOLM procedure
F2	Sensitivity	Test only if any Ho for F2 is rejected, p-value adjusted using HOLM procedure
	Specificity	Test only if any Ho F2 is rejected, p-value adjusted using HOLM procedure

The average glandular dose (i.e., radiation dose) refers to the total radiation dose during the exam and is expressed in mGy. The goal is to compare total radiation dose between the Philips MicroDose tomosynthesis system and the FFDM systems. The following hypothesis will be tested:

The average glandular dose (AGD) will be recorded per subject for each breast (right and left) and view (CC and MLO). The following hypothesis will be evaluated:

- Null Hypothesis: $H_0: \mu_2 - \mu_1 > \delta$
- Alternative Hypothesis: $\mu_2 - \mu_1 \leq \delta$

where μ_1 and μ_2 are the mean average glandular dose (i.e., radiation dose) for the Philips MicroDose Tomosynthesis system and FFDM system, respectively, and δ is 10% of the FFDM radiation dose.

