Analysis will be performed using an appropriate analysis of variance. If the required assumptions for the ANOVA are violated, transformation of the data or non-parametric procedures may be used. The 95% confidence interval for the mean difference in radiation dose between the two systems will be constructed. Under this proposal Philips tomosynthesis will be declared as emitting less radiation than the FFDM if the upper bound of the 95% confidence interval for the difference in radiation dose is less than 10% of the FFDM.

The non-cancer recall rate will be recorded per subject. All negative screening, recalled and benign biopsy cases will be included. The following hypothesis will be evaluated:

- Null Hypothesis: $H_0: \pi_2 - \pi_1 = 0$
- Alternative Hypothesis: $\pi_2 - \pi_1 \neq 0$

where π_1 and π_2 are the non-cancer recall rate for the Philips MicroDose Tomosynthesis system and FFDM system, respectively.

Recall rate will be analyzed using the concept of clustered binary data as described by Zhou et al (2011). In this case, each Reader will be considered as multiple observations within the same subject (cluster). The 95% confidence interval for the difference in recall rate will be constructed. If the upper limit to the one-sided 95% Confidence Interval for the difference (Philips minus FFDM) in recall rates among non-cancers is less than 0.05 (delta of 5%), Philips tomosynthesis will be considered as resulting in a similar recall rate to that of 2D FFDM. In addition, a bootstrapping method with replacement will be used to compare average recall rates among all Readers.

The sensitivity or specificity within a reader between the two systems will be estimated, and tested for statistical significance using binomial test for paired data. Results will be summarized across readers using the ANOVA model of Obuchowski and Rockette [11], which applies to any metric of diagnostic accuracy under general conditions. The following hypothesis will be evaluated:

- Null Hypothesis: $H_0: S_2 - S_1 \geq 0.10$

Philips Mammography Solutions Sweden	Clinical Investigation Plan Comparison of the Philips MicroDose Tomosynthesis System to 2D Digital Mammography	DOC-MTIN-9RWH8K- 8.0 Page 31 of 38
---	---	--

- Alternative Hypothesis: $S_2 - S_1 < 0.10$

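### The dose margin in 6.8 is 10% of the FFDM mean but is tested with an interval for the plain difference; if the margin comes from the study's own exams, the one-sided error is not the nominal 2.5%

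*Combined protocol and SAP*

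**What the plan says.** Sections 4.2 and 6.8 state the dose hypothesis on mean average glandular dose, with μ1 for Philips and μ2 for FFDM, and a margin δ that "is 10% of the FFDM radiation dose". Neither section attaches a value in mGy to δ.

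Section 6.8 then gives the analysis: "The 95% confidence interval for the mean difference in radiation dose between the two systems will be constructed". Philips is declared the lower-dose system "if the upper bound of the 95% confidence interval for the difference in radiation dose is less than 10% of the FFDM". No ratio and no weighted contrast is named as the main method. If the ANOVA assumptions fail, "transformation of the data or non-parametric procedures may be used".

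The data are paired. Section 5.1 has each woman imaged on both systems ("4-view mammograms on a FDA cleared FFDM system will be collected"), and section 5.5.3 says "Average Glandular radiation dose will be read out from the DICOM header for each mammogram".

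Section 6.1.2 sizes the comparison "using a paired t-test with a 0.025 one-sided significance level", with an SD of the difference of about 1.5 mGy, about 100 subjects and a difference of about 0.5 mGy, described as 10% of the overall dose.

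**The concern.** A margin of 0.10 × μ2 is an unknown quantity. If it is replaced by 0.10 times the FFDM mean observed in the trial, the rule is in effect a test on mean(P) - 1.1 × mean(F), or 0.9 in place of 1.1 for the other direction. Yet the standard error it uses belongs to mean(P) - mean(F). Those standard errors differ, so the limit is not calibrated at the boundary of the hypothesis.

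The dose endpoint matters beyond itself. It shares a Holm-adjusted family with recall rate, and rejecting either null lets sensitivity and specificity be tested. Section 6.8 sets up that procedure in order to control the Type I error, so a miscalibrated dose test weakens that control. The rule also supports a statement about radiation dose.

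**Working it through.** **Inputs from the plan (6.1.2).** SD of the paired difference 1.5 mGy; about 100 subjects; difference 0.5 mGy; one-sided 0.025. Per-breast FFDM SDs are 1.1 mGy (GE) and 0.7 mGy (Hologic).

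**Inputs assumed.** The documents give no whole-exam SD for either system separately and no correlation. FFDM whole-exam SD s_F: 1.4 to 2.2 mGy (twice the per-breast SDs). Philips/FFDM SD ratio: 0.5 to 1.1. The correlation r then follows from the 1.5 mGy.

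**Step 1: the plan's power.** Noncentrality = 0.5 / (1.5/√100) = 3.33. Power = Φ(3.33 - 1.96) = 0.915 (0.910 by noncentral t). N for 80% power is 71 (73 by t). The stated power above 80% is reproduced.

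**Step 2: the real error of the rule.** At the boundary,

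error = Φ(-1.96 × SD(P - F) / SD(P - kF)), with k = 1.1 for a +10% margin and k = 0.9 for a -10% margin.

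Both standard errors fall as 1/√n, so n cancels.

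Var(P - 1.1F) = Var(P - F) + 0.21 s_F² - 0.20 r s_P s_F.

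Var(P - 0.9F) = Var(P - F) - 0.19 s_F² + 0.20 r s_P s_F.

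With Var(P - F) = 1.5² = 2.25, r s_P s_F = (s_P² + s_F² - 2.25)/2. So

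Var(P - 1.1F) = 2.475 + 0.11 s_F² - 0.10 s_P²,

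Var(P - 0.9F) = 2.025 - 0.09 s_F² + 0.10 s_P².

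Example, s_F = s_P = 1.4 (r = 0.426): Var(P - 1.1F) = 2.475 + 0.2156 - 0.196 = 2.495, SD 1.579. Error = Φ(-1.96 × 1.5/1.579) = Φ(-1.861) = 3.1%.

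| s_F | s_P/s_F | r | error, +10% | error, -10% |
|---|---|---|---|---|
| 1.4 | 0.5 | 0.10 | 3.5% | 1.6% |
| 1.4 | 1.0 | 0.43 | 3.1% | 2.0% |
| 1.4 | 1.1 | 0.48 | 3.0% | 2.1% |
| 2.2 | 0.5 | 0.79 | 4.2% | 1.2% |
| 2.2 | 1.0 | 0.77 | 3.2% | 2.1% |
| 2.2 | 1.1 | 0.79 | 2.9% | 2.3% |

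Taking the difference as FFDM minus Philips, as the hypotheses are written, involves the same contrast P - 0.9F with its sign changed, so the last column applies to that reading too. If the interval is one-sided 95%, the +10% error is 5.6-7.3% against a nominal 5%.

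**Step 3: simulation.** With normally distributed doses, +10% margin, 100,000 trials per setting and n = 100 or 400, the error was 3.1-3.4% with the estimated margin, 2.4-2.6% with a truly fixed margin, and 2.5-2.6% for the paired contrast. The excess did not shrink at n = 400.

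**Step 4: direction.** On the +10% reading the excess disappears when 0.21 s_F = 0.20 r s_P, that is r × s_P/s_F = 1.05, and reverses beyond that. For example, s_F = 1.4, s_P = 2.0, r = 0.9 gives SDs of 0.959 for P - F, 0.910 for P - 1.1F and 1.025 for P - 0.9F. The errors are 1.9% for +10% and 3.3% for -10%. The SD of the difference there is 0.96 mGy, not the plan's 1.5.

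**The case against.** Section 6.8 does not say outright that the percentage is taken of the FFDM mean observed in these women, and 6.1.2 does give a figure in mGy. If 0.5 mGy was meant as a fixed margin, the error rate is nominal. That stands as a condition on the finding. It does not remove the finding, because 6.1.2 uses 0.5 mGy as an approximate planning difference and nowhere names it as the test margin.

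The practical effect is also small. The per-breast doses in 6.1.2 (1.86 against 2.91 and 3.03 mGy) imply savings of 36% (1 - 1.86/2.91) to 39% (1 - 1.86/3.03) for MicroDose, far from either boundary. This stands too.

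Four stronger readings are tempting, and the documents do not support them:

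- *The error is always inflated for +10% and always too low for -10%.* Step 4 shows a reversal when the Philips dose is much more variable and highly correlated with FFDM. The plan does not give the SDs and correlation that would settle it.
- *The dose test alone opens the later hierarchy.* Recall rate shares its family, and either rejection is enough.
- *An mGy margin means nothing under the transformation or rank fallback.* A percentage margin has a log-scale counterpart, and a rank-based shift estimate is in mGy.
- *A paired log-ratio test is an equivalent cure.* It compares geometric means, whereas the hypothesis is on arithmetic means. In lognormal simulations at the arithmetic-mean boundary (FFDM mean 6 mGy assumed, n = 100), its error was about 0.03% for +10% (SDs 2.0 FFDM and 1.2 Philips, r 0.7) and 6.4% for -10% (both SDs 2.0).

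**Conclusion.** The concern holds, conditionally and at modest size. If the 10% is taken of the trial's own FFDM mean, the rule in 6.8 uses the wrong standard error and its one-sided error is not 2.5% at any sample size. At the plan's SD of the difference it is about 2.9-4.2% on a +10% reading and 1.2-2.3% on a -10% reading, over assumed SDs that the documents do not supply. The -10% figures mean lost power, not a false claim.

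The sample size is not threatened, and a saving near 40% would give the same conclusion under either rule. Which column applies cannot be settled until the plan reconciles its own direction: the hypotheses run FFDM minus Philips, while the decision rule treats an upper bound below 10% of FFDM as showing less radiation. This is a correction worth making before analysis, not a threat to the study.

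**What to change.** First reconcile the direction of the dose hypothesis with the decision rule in 6.8. Then do one of two things:

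- Replace the rule with a paired confidence interval for the per-woman contrast D = Philips total - 1.10 × FFDM total (or 0.90 ×, according to the direction settled), compared with 0.
- Prespecify the margin as a fixed value in mGy and keep the interval for the plain difference.

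If a log-scale analysis is kept as the fallback, say that it estimates a ratio of geometric means, and do not describe it as equivalent.

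Once the direction is settled, the change is a sentence in 6.8, with the same data and no added subjects. The downside is a slightly wider interval on the +10% reading. With equal SDs the contrast SD is 1.58-1.59 mGy in place of 1.5. Power at n = 100 for a 0.5 mGy distance falls from about 0.915 to 0.88-0.89, and N for 80% power rises from about 71 to 79-80, within the planned 100. The contrast keeps the usual sensitivity of a t interval to skewed doses, but that fades as n grows, whereas the present error does not.

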4.2. Secondary Objectives

The secondary objectives are:

- To compare the average glandular dose for exams acquired on Philips MicroDose Tomosynthesis system and the 2D mammography system.
- To compare the non-cancer recall rate for Philips MicroDose Tomosynthesis system and 2D mammography exams.
- To compare the sensitivity and specificity of the Philips MicroDose tomosynthesis system (i.e., Tomosynthesis and synthetic 2D) to that obtained with 2D mammography.

The average glandular dose (AGD) will be recorded per subject for each breast (right and left) and view (CC and MLO). The following hypothesis will be evaluated:

- Null Hypothesis: $H_0: \mu_2 - \mu_1 > \delta$
- Alternative Hypothesis: $\mu_2 - \mu_1 \leq \delta$

where μ_1 and μ_2 are the mean average glandular dose (i.e., radiation dose) for the Philips MicroDose Tomosynthesis system and FFDM system, respectively, and δ is 10% of the FFDM radiation dose.

The non-cancer recall rate will be recorded per subject. The following hypothesis will be evaluated:

- Null Hypothesis: $H_0: \pi_2 - \pi_1 = 0$
- Alternative Hypothesis: $\pi_2 - \pi_1 \neq 0$

where π_1 and π_2 are the non-cancer recall rate for the Philips MicroDose Tomosynthesis system and FFDM system, respectively.

Sensitivity will be estimated for each reader as the proportion of cancer cases with per-case BI-RADS category 4 or higher. Specificity will also be estimated by reader as the proportion of non-cancer cases with per-case BI-RADS category less than 4. Ground truth will be based on biopsy results or the outcome for the woman after one year follow-up.

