Where Θ_1 is the average AUC for readers using the Philips MicroDose System (tomosynthesis + synthetic 2D) and Θ_2 is the average AUC for readers using the FFDM System. The Philips MicroDose tomosynthesis system will be considered non-inferior to the FFDM if the upper limit one-sided 95% CI for the difference in AUCs is less than 0.05. AUC for Philips MicroDose tomosynthesis system and the FFDM will be also be presented by readers.

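### The dose rule lets Philips claim lower radiation without showing it, and the plan's three statements of the dose comparison disagree

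*Combined protocol and SAP*

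**What the plan says.** The dose comparison is stated in three places.

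- **Hypotheses (4.2, repeated in 6.8).** The null is "Null Hypothesis: $H_0: \mu_2 - \mu_1 > \delta". Here μ1 stands for Philips and μ2 for FFDM; in the plan's words these "are the mean average glandular dose (i.e., radiation dose) for the Philips MicroDose Tomosynthesis system and FFDM system, respectively". The margin δ is 10% of the FFDM dose. The null is therefore that Philips saves more than 10%, and the alternative is that it saves 10% or less.
- **Decision rule (6.8).** The conclusion is worded "Philips tomosynthesis will be declared as emitting less radiation than the FFDM". The condition for reaching it is an "upper bound of the 95% confidence interval for the difference in radiation dose is less than 10% of the FFDM". Neither an order of subtraction nor a sign on the 10% is given.
- **Sample size (6.1.2).** The null is that the two systems give the same dose. About 100 subjects are said to give more than 80% power for 0.5 mGy, taken as 10% of the patient's total, with an SD of the difference of 1.5 mGy and a paired t-test at one-sided 0.025.

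The recall rule, also in 6.8, does state a direction: its limit is "for the difference (Philips minus FFDM) in recall rates among non-cancers is less than 0.05", and the conclusion it allows is only that the recall rates are similar.

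Dose shares a Holm-adjusted family with recall rate, tested after AUC. Sensitivity and specificity then carry the condition "Test only if any Ho for F2 is rejected, p-value adjusted using HOLM procedure".

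**The concern.** A claim of lower dose needs a confidence limit that excludes equal dose. A limit below a positive margin excludes only an excess larger than that margin. The rule in 6.8 sets a limit of the latter kind but concludes that the dose is lower.

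The written hypotheses do not rescue it. If the rule follows their order of subtraction, the claim is made only when a saving of 10% or more has been ruled out, which is close to the opposite of what the words say. The null in 6.1.2 matches neither.

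Two things are at stake. A statement about radiation could be made for a device that does not lower it, or withheld from one that does. And because rejecting the dose null can open the gate to sensitivity and specificity, an undefined rejection leaves that gate undefined too. Those two endpoints would still face their own Holm-adjusted tests.

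**Working it through.** **Inputs**

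- From 6.1.2: n = 100; SD of the paired difference 1.5 mGy; one-sided 0.025.
- FFDM exam total: 5 mGy (if 0.5 mGy is 10%) up to 7.2 mGy (2 × 3.6 mGy per breast, site data in 6.1.2).
- Philips exam total: 3.72 mGy (2 × 1.86 per breast, 6.1.2) or 3.2 mGy (4 views × 0.8 mGy, 3.3.6).
- Assumed: the SD applies to the exam total at every FFDM level, and the margin, 0.1 × FFDM, is treated as fixed.

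**The plan's own figure.** SE = 1.5/√100 = 0.15 mGy. For a 0.5 mGy difference the noncentrality is 0.5/0.15 = 3.33, and power from the noncentral t is 0.910. The smallest n for 80% power is 73. The sample size statement in 6.1.2 reproduces.

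**Expected saving against the written null.** Per breast, 1 − 1.86/2.91 = 36% and 1 − 1.86/3.03 = 39%. Per exam this is 5.82 − 3.72 = 2.10 mGy and 6.06 − 3.72 = 2.34 mGy, against δ of 0.58 and 0.61 mGy. Over all pairings of the inputs the saving runs from 1 − 3.72/5 = 26% to 1 − 3.2/7.2 = 56%. All of these lie inside the null of 4.2 and 6.8.

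**Reading 1: Philips minus FFDM.** The claim is made when the upper limit is below the margin:

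P(claim) = P(T < −t(0.975, 99)), where T is noncentral t with 99 df and noncentrality (true difference − margin)/0.15.

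| True Philips − FFDM | Rule, FFDM 5 mGy | Rule, FFDM 7.2 mGy | Superiority (margin 0) |
|---|---|---|---|
| 0 | 0.910 | 0.997 | 0.025 |
| +5% | 0.379 | 0.662 | at most 0.00015 |
| 26% to 56% saving | about 1 | about 1 | about 1 |

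At 5 mGy and +5%, for example, the noncentrality is (0.25 − 0.50)/0.15 = −1.67. The half-width of the interval is 1.984 × 0.15 = 0.298 mGy, so an observed Philips excess of up to 0.50 − 0.298 = 0.202 mGy still earns the claim. If the limit is read as one-sided 95%, as in the recall rule, the zero-difference figures become 0.952 to 0.999, against 0.05 for superiority.

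**Reading 2: FFDM minus Philips.** At zero difference the figures are the same. At a 26% saving with FFDM at 5 mGy, the noncentrality is (1.30 − 0.50)/0.15 = 5.33 and the probability of the claim is below 10⁻¹². For a device 0.5 mGy higher than FFDM it is about 1.

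**If 1.5 mGy were a per-breast SD.** The exam SD could then reach 3.0 mGy. On reading 1 the claim would be made with probability 0.38 to 0.66 at zero difference and 0.13 to 0.22 at +5%.

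**The case against.** The best defence is that this is a slip in copying a template. The AUC hypothesis in 4.1 has the same form, FFDM minus Philips in the null, where higher is better. Reverse the inequality for dose and the hypotheses become a test that Philips saves more than 10%, for which the claim of lower radiation fits. That may be what was intended, and such a test would have power above 0.999 at a 26% saving. But it is a repair, not a reading of the current text: the inequality and the confidence bound would both have to be rewritten, and 6.1.2 would still state another null.

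Three smaller points stand in part.

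- **Analysis set.** The plan does not fix it at 100; about 405 cases are read and about 800 women imaged. Larger numbers make the mislabelling worse: at +5% on reading 1, the claim is made with probability 0.92 to 0.998 at n = 405 and 0.997 or more at n = 800.
- **Expected saving.** The 36–39% figure is for Philips MicroDose against two other vendors. It reaches the tomosynthesis device only through 3.3.6, which calls its radiation comparable to MicroDose SI. The abbreviation list counts MicroDose SI L50 among FFDM units, and against that comparator little saving would be expected. The near-equal case is then a realistic one.
- **Weight.** The endpoint is secondary. On reading 1, at the expected saving, the rule and a superiority test give the same answer.

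**Conclusion.** The concern holds. The direction, the null, the margin and the claim do not fit together, and the rule does not support its conclusion under either order of subtraction.

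On the more plausible reading, Philips minus FFDM as in the recall rule, the harm is confined to the label. The 0.91 to 0.997 at equal dose is simply the power of a 10% non-inferiority test; the fault is calling a success *less radiation*. On the literal sign of the hypotheses, the expected saving cannot be declared.

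The probabilities rest on n = 100, an exam-level SD of 1.5 mGy, an FFDM total of 5 to 7.2 mGy and a fixed margin. The textual conflict does not depend on them. The 6.1.2 sample size is not at fault and the primary AUC analysis is untouched. This should be corrected before analysis, because choosing the sign or the claim after seeing the data would undermine the pre-specified testing order.

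**What to change.** In 4.2, 6.1.2 and 6.8, define the difference once as Philips minus FFDM and use one null with a matching claim. The sponsor must choose:

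- **Superiority.** H0: μ1 − μ2 ≥ 0; lower radiation is declared only if the upper limit is below 0.
- **Non-inferiority.** H0: μ1 − μ2 ≥ +δ; the claim is limited to a dose no more than 10% above FFDM.

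If a saving of more than 10% was the intended claim, that is a third form, H0: μ1 − μ2 ≥ −δ with the upper limit below −δ, and it needs its own power statement.

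Also state the one-sided level passed to the dose and recall family. The 6.8 table says "Test at the 0.05 level, no adjustment to the p-value" for AUC, 6.6 uses the "upper limit one-sided 95% CI for the difference in AUCs is less than 0.05", and 6.1.2 powers dose at one-sided 0.025.

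The cost is wording; no new data are needed. For superiority with a 0.5 mGy saving, or non-inferiority with δ = 0.5 mGy and no true difference, the arithmetic is the same. With 100 subjects, power is 91% at one-sided 0.025 (the first Holm step if the family level is one-sided 0.05) and 85% at 0.0125 (the first step if it is 0.025). For 80% power, 73 and 89 subjects are needed. This assumes the 1.5 mGy SD applies to the exam total. At 3.0 mGy, power for 0.5 mGy with 100 subjects would be 38% at one-sided 0.025, so 6.1.2 should state the unit of the SD.

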6.1.3. Sample Size Justification for Recall Rate

Based on the outcome of the most recent tomosynthesis PMA (i.e., MAMMOMAT Inspiration with Tomosynthesis, P140011), the recall rate for A FFDM alone was 0.438. For this study, a similar recall rate is expected. Assuming that a 5% reduction in recall rate for tomosynthesis is clinically significant and adjusting for the multiple endpoints, a total of 2300 cases will allow for approximately 80% to detect an improvement in recall rate of approximately 5%. Furthermore, assuming that the correlation among readers reading the same case in approximately 0.5, and that all subject will be read by all 18 readers, approximately 250 subjects will be required.

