6.1.5. Sample Size Justification for Specificity Non-inferiority Analysis

For specificity analysis, similar to sensitivity analysis, the following assumptions were made:

- The type I error: $\alpha = 0.05$
- Specificity for control test: $S_p = 0.70$
- Number of positive patients: $n_2 = 300$
- Non-inferiority margin: $\Delta = 0.10$
- Variability between readers: $\sigma_b^2 = 0.012$
- Variability within the reader: $\sigma_w^2 = 0.003$
- Correlations: $\rho_1 = 0.46$, $\rho_2 - \rho_3 = 0$
- Correlation: $\rho_b = 0.8$
- Power for the non-inferiority test: $1 - \beta \geq 0.8$

Similar to sensitivity analysis, the variance between different patients σ_c^2 will be calculated based a binomial assumption, as described above.

In a previous study on the Philips MicroDose L30, the estimated specificity was 0.764, with a 95% C.I. (0.688, 0.841) [19]. In another similar study for the Hologic Tomosynthesis Mammography System, the specificity for a 2D system was 0.651 [20]. Based on these previous results, it is assumed that the specificity for the control test is approximately 0.70.

Also, in a previous study on Philips MicroDose L30 [19], the estimated σ_b^2 with 95% C.I. was 0.0087 (0.0047, 0.0208). In another similar study for the Hologic Tomosynthesis Mammography System [20], the estimated σ_b^2 with 95% C.I. was 0.0144 (0.0077, 0.0357). Thus a value of 0.012 is a reasonable estimation for σ_b^2 for the proposed study.

The variance within each reader interpreting the results of the same patients σ_w^2 is estimated as one-fourth of σ_b^2 , thus 0.003.

Philips Mammography Solutions Sweden	Clinical Investigation Plan Comparison of the Philips MicroDose Tomosynthesis System to 2D Digital Mammography	DOC-MTIN-9RWH8K- 8.0 Page 28 of 38
---	---	--

Correlation for the same patients evaluated by the same reader using different tests (ρ_1), for the same patients evaluated by different readers with the same tests (ρ_2) and for the same patients evaluated by different readers and different tests (ρ_3) are based on suggestions from Obuchowski [11]. The correlation for the same reader to evaluate patients using different tests ρ_b ranges from 0.44 to 0.86 in AUC analysis, according to Rockette [18] such correlation are usually higher for sensitivity/specificity analysis. Thus, it is safe to assume the expected value ρ_b to be 0.80 in the proposed study.

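### The recall analysis in section 6.8 clusters by woman only and leaves out reader-by-modality variance, so its interval, test and 0.05 rule do not extend beyond the 18 study readers

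*Combined protocol and SAP*

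**What the plan says.** Section 6.8 on recall: "Recall rate will be analyzed using the concept of clustered binary data". The unit is then fixed: "each Reader will be considered as multiple observations within the same subject (cluster"). Three results rest on this: a 95% interval, a two-sided test of equal recall rates, and a rule that calls recall similar when the upper one-sided 95% limit for Philips minus FFDM lies below 0.05. The section adds that "a bootstrapping method with replacement will be used to compare average recall rates among all Readers", but gives no resampling unit and no place for it in the decision rule.

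In the gatekeeping table, recall shares the first secondary family with radiation dose: "Test only if Ho for AUC ROC is rejected, p-value adjusted using HOLM procedure".

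The other reader endpoints are handled differently. Section 6.6 gives AUC random reader effects. Section 6.8 assigns sensitivity and specificity to the Obuchowski-Rockette model, "which applies to any metric of diagnostic accuracy under general conditions". Section 5.4.4 chooses a mix of general and specialist readers so that they stand for future users.

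**The concern.** Every reader reads every woman on both systems. Clustering by woman accounts for different readers agreeing on the same woman. It cannot see a shift in one reader's recall threshold between modalities, because that shift touches all of that reader's women alike and adds almost nothing to the variation between women. The plan's own model in section 6.1.1 has a random reader-by-test interaction for exactly this; the recall analysis drops it.

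Non-cancer recall is also close to one minus specificity. Recall means BI-RADS 3 to 5 with a confidence score of 51 to 100 (sections 5.4.2 and 5.4.2.2), and specificity is cut at BI-RADS 4 (section 4.2). The same readers, women and readings would thus get two incompatible variance models.

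At stake are a recall claim that may belong to this panel of readers, and the Type I error control of the gatekeeping scheme, since a rejection on recall is one of two ways to open the sensitivity and specificity tests.

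**Working it through.** **The plan's own recall figure (section 6.1.3).** The plan goes from 2,300 cases, 18 readers and an inter-reader correlation of 0.5 to about 250 subjects.
- The usual design effect is 1 + 17 × 0.5 = 9.5, which gives 2,300 × 9.5 / 18 = 1,214 subjects.
- About 250 appears only as 2,300 / (18 × 0.5) = 256.

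The figure is therefore not reproduced. That is a separate matter. What counts here is that this calculation also has no reader variance.

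**Inputs for the check.**
- Readers J = 18; non-cancers n = 300 + 40 = 340 (section 5.3.4).
- Recall p = 0.438 (section 6.1.3: "the recall rate for A FFDM alone was 0.438").
- Assumption: the specificity values of section 6.1.5 apply to recall. These are between-reader variance σ_b² = 0.012, ρ_b = 0.8, ρ₁ = 0.46, ρ₂ − ρ₃ = 0 and within-reader variance σ_w² = 0.003.

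**Formula.** From the non-centrality parameter in section 6.1.1, with one reading occasion:

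Var(difference) = (2/J) × {σ_b²(1 − ρ_b) + σ_w² + σ_c²[(1 − ρ₁) + (J − 1)(ρ₂ − ρ₃)]}, where σ_c² = p(1 − p)/n.

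σ_c² = 0.438 × 0.562 / 340 = 0.000724, so the case term is 0.000724 × 0.54 = 0.000391. The reader-by-modality term is 0.012 × 0.2 = 0.0024. Clustering by woman keeps only the case term.

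| Terms counted | Sum in braces | SE | Ratio |
|---|---|---|---|
| Cases only | 0.000391 | 0.0066 | 1 |
| + reader-by-modality | 0.002791 | 0.0176 | 2.7 |
| + within-reader (upper bound) | 0.005791 | 0.0254 | 3.9 |

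**Effect on the test and the rule.** If the true SE is k times the one used, a nominal 5% two-sided test rejects with probability 2Φ(−1.96/k). At a true increase of 5 points, the similarity rule passes with probability Φ(−1.645/k). The within-reader term is left out here.

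| ρ_b | ρ₂ − ρ₃ | k | Two-sided rejection | False "similar" |
|---|---|---|---|---|
| 0.80 | 0 | 2.67 | 46% | 27% |
| 0.86 | 0 | 2.30 | 39% | 24% |
| 0.95 | 0 | 1.59 | 22% | 15% |
| 0.44 | 0 | 4.26 | 65% | 35% |
| 0.80 | 0.05 | 1.84 | 29% | 19% |
| 0.80 | 0.10 | 1.57 | 21% | 15% |
| 0.95 | 0.10 | 1.17 | 9% | 8% |

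The plan quotes 0.44 to 0.86 as the range of ρ_b for AUC. The value 0.95 and the non-zero ρ₂ − ρ₃ are favourable assumptions. The last row combines both.

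**Simulation.** In crossed reader-by-case probit data with no true difference, the woman-clustered 5% test rejected 24 to 53% of the time across the settings tried without a separate within-reader shift. A crossed reader-and-case analysis rejected about 4 to 5%. With no reader-by-modality variance, the woman-clustered test held its level (5.2%).

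**Power with readers random.** For a 5-point difference, F(1, 17) with non-centrality 0.05²/SE² = 0.0025/0.000310 = 8.06:

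| Non-cancers | Two-sided 0.05 | Two-sided 0.025 (Holm's first step) |
|---|---|---|
| 250 | 0.74 | 0.63 |
| 340 | 0.76 | 0.65 |
| Unlimited | 0.82 | 0.72 |
| 340, within-reader term fully counted | 0.46 | 0.34 |

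**The case against.** **Reader differences cancel.** A reader might infer that ordinary differences in recall threshold among the 18 readers would pass for a device effect. The documents do not support that. The design is paired, so a reader's overall level drops out, and without reader-by-modality variance the planned test is sound. Only the interaction is lost. But the plan itself sets ρ_b at 0.8 for specificity, not at 1.

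**The largest figures.** It is also tempting to quote the SE of 0.0254, which adds the within-reader variance. Independent noise over 340 yes/no calls cannot exceed 0.438 × 0.562 / 340 = 0.0007, so a value of 0.003 must be mostly a shift shared within an occasion. Under section 5.4.3 each session contains both modalities, with the case groups swapped in the second. A session-wide shift then largely cancels if the groups are of similar size. That SE is at most an upper bound.

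**Borrowed inputs.** The plan gives no reader variance for recall, and recall is cut one BI-RADS category lower than specificity. This stands: the direction is firm wherever reader-by-modality variance exists, but the size is uncertain.

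**The bootstrap.** It might resample readers. Since its unit is not stated, it can be neither credited nor dismissed, and it does not drive the decision.

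**Rank.** Recall is tested only after AUC succeeds, dose alone can also open the next family, and half of the false two-sided rejections would go against the device. All of this stands and limits the severity.

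**Conclusion.** The point holds for the reader-by-modality term. As written, the recall interval, test and similarity rule support a conclusion about these 18 readers only, which is narrower than the reader selection and the other reader analyses intend.

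On the borrowed specificity values the standard error is 2.7 times too small for the wider conclusion. The ratio runs from about 1.6 to 4.3 when one input is varied at a time, and falls to 1.2 only if both favourable assumptions hold together. With ρ_b of 0.8 or more, again varying one input at a time, the two-sided error is roughly 20 to 45%, and a true 5-point increase would be called similar about 15 to 27% of the time instead of 5%.

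A reader might infer that the main result is compromised. It is not: the AUC analysis has random readers and is tested first. This is a change that should be made to a gated secondary endpoint.

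**What to change.** In section 6.8, analyse each reader's non-cancer recall proportion (BI-RADS 3 or higher, confidence score 51 or higher) with the random-reader, random-case Obuchowski-Rockette model already planned for sensitivity and specificity. Base the interval, the test and the 0.05 rule on it. If the bootstrap stays, state that readers and women are resampled jointly.

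Restate recall power in section 6.1.3 under the same model, at the Holm level, with the variance assumptions for recall written out.

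No new data or software are needed. The cost is a wider interval and a stated power below 0.80. More cases alone would not restore it: at Holm's first step, power stays near 0.72 even with unlimited cases, because the number of readers is the limit. The sponsor should accept that openly, or revisit the number of readers before reading starts.
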